5.12 Prior and Concomitant Medication

Medication start and stop dates will be compared to the date of first dose of study medication to allow medications to be classified as either prior or concomitant and will be recorded up to Day 29. If the start and/or stop dates of medications are missing or partially missing, the dates will be compared as far as possible with the date of administration of study drug. Medications starting after the completion/withdrawal date will be listed but will not be classified or summarized.

Medications that start and stop prior to the date of first dose of study medication will be classified as prior only.

A medication will be regarded as concomitant if it started on or after the date of first dose of study treatment.

A medication will be regarded concomitant if:

- it started prior to date of first dose of study treatment but was ongoing at the time of the first dose of study treatment.
- the start date of medication is completely unknown.

Medications are coded prior to delivery of the validated clinical data base. The following describes this process.

Drugs are coded to the WHO Drug entry that best represents (most accurately and specifically) the reported term. If a reported term is a trade name, then it will generally be coded to the trade name entry in WHO Drug that contains the correct active ingredients for that trade name. If a reported term is a generic name, then it will generally be coded to the generic entry in WHO Drug with that ingredient or combination of ingredients.

A WHO Drug entry may have one or more ATC (Anatomic-Therapeutic-Chemical) codes assigned to it within the dictionary. If a WHO Drug entry has only one ATC code, then that ATC code is additionally returned for that WHO Drug entry. If a WHO Drug entry has more than one ATC code assigned, then a single ATC code is selected based on the most common usage for the drug and the selected ATC code is additionally returned for the WHO Drug entry.

Separate sets of tables will be provided for non-antimicrobial or non-nephrotoxic medications, antimicrobial medications, and nephrotoxic medications.

6 Safety Analysis

The primary safety measures are AEs (including SAEs), deaths, clinical safety laboratory, PE, and vital signs through Day 29 including determination of survival through Day 29.

The safety profiles will be compared between active and placebo groups using descriptive statistics as appropriate for continuous and categorical safety variables. Changes in continuous safety measures such as laboratory values will be summarized by mean changes over time using descriptive statistics (sample size (N), mean, SD, median, minimum and maximum). The presence of clinically significant safety findings will be summarized by shift tables separately for each group using counts and percentages. AEs will be classified according to system organ class and preferred term and summarized by counts and percentages separately for those recorded on Day 0 (prior to drug administration) and those with onset on Day 1 or later. AEs will also be summarized by relationship to study drug, severity, and whether they are serious. Specific summaries will involve AEs and SAEs in the Infection/Infestation system organ class. Vital signs including weight, temperature, systolic BP, diastolic BP, respiration rate, and heart rate will be summarized across time (Day 0, Day 1, Day 2, Day 3, Day 7, Day 10, Day 14, Day 21 and Day 29) and separately by treatment group by N, Mean, and SD.

6.1 Adverse Events

Treatment emergent adverse events (TEAEs) are defined as those with onset on Day 1 or later. TEAEs will be classified according to system organ class and preferred term and summarized by counts and percentages. TEAEs will also be summarized by relationship to study drug, severity, and whether they are serious. AE recorded prior to study drug administration will be included in listings but not included in summary tables.

6.2 Laboratory Values

6.2.1 Description of Value Over Time

Laboratory values over time including blood chemistry and hematology will be summarized using descriptive statistics and compared between treatment groups. Values over time and changes over time will be summarized.

6.2.2 Laboratory Shift Tables

The presence of clinically significant changes in laboratory values will be further evaluated using shift tables for blood chemistry and blood hematology changes from screening to Day 7 and from screening to Day 14. These tables will summarize the numbers and percentages of patients that went from a lab value in the normative range at screening to one that is in the higher than normal range or lower than normal range.

6.2.3 Treatment of Clinical Laboratory Abnormalities

Deterioration as compared to baseline in protocol mandated laboratory values, vital signs and other safety variables will only be reported as AEs only if they fulfill any of the SAE criteria or are the reason for discontinuation of treatment with the investigational medical product. However, the Investigator may record such findings as an AE at his/her discretion in addition

to completing an unscheduled laboratory/vital signs eCRF with the information on the clinically significant test abnormality. If a deterioration in a laboratory value/vital sign is associated with clinical signs and symptoms, the sign/symptom will be reported as an AE and the associated laboratory result/vital sign will be considered as additional information. Any new or aggravated clinically relevant abnormal medical finding at a PE, dermal examination or lung auscultation as compared with the baseline assessment will be reported as an AE. Clinically relevant deterioration in unscheduled assessments of laboratory or vital sign parameters should be reported on additional eCRF pages.

Wherever possible, the reporting Investigator uses the higher level medical concept, rather than the laboratory term (e.g., anemia versus low hemoglobin value).

Additionally, for blood chemistry and blood hematology, results at each visit will be summarized according the frequency of “Critical High”, “Above”, “Within”, “Below”, and “Critical Low” results.

6.3 Physical Exams

Physical exam data on Days 1, 7, and 10 will be summarized in patient specific listings.

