12.12 Safety Analysis

The primary safety measures are AEs (including SAEs), clinical safety laboratory, PE, vital signs through Day 28 and including determination of survival through Day 28.

The safety profiles will be compared between active and placebo groups using descriptive statistics as appropriate for continuous and categorical safety variables. Changes in

continuous safety measures such as laboratory values will be summarized by mean changes over time using descriptive statistics (mean, SD, median, minimum and maximum). The presence of clinically significant safety findings will be summarized by shift tables separately for each group using counts and percentages. AEs will be classified according to system organ class and preferred term and summarized by counts and percentages separately for those recorded at Screening (prior to drug administration) and those with onset on Day 1 or later. AEs will also be summarized by relationship to study drug, severity, and whether they are serious. Specific summaries will involve AEs and SAEs in the Infection/Infestation system organ class. Results from PEs will be tabulated for the Screening, Day 7, and Day 14. For each test, the number of patients evaluated, and the numbers and percentages of patients with Normal and Abnormal results will be tabulated. Vital signs including weight, temperature, systolic BP, diastolic BP, respiration rate, and heart rate will be summarized across time (Screening, Day 1, Day 2, Day 3, Day 7, and Day 14 separately by treatment group by N, Mean, and SD.

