9.6 Physical Examinations

Results from physical examinations will be provided in the patient listings.

10 Deviations from the Original Statistical Plan

Any deviations from the original statistical plan will be described and justified in the final report.

11 Appendix 1: Tables and Listing TOC

		Enrollment
1	14.1.1.1	Number of Patients by Site Screened and by Analysis Set
2	14.1.1.2	Numbers of Patients by Site, Treatment Group, and Analysis Set
3	14.1.1.3	Number of Patients by Site, Treatment Group, and Randomization Stratum Modified Intent-to-Treat (mITT) Analysis Set
4	14.1.1.4	Number of Patients by Site, Treatment Group, and Randomization Stratum As Treated (Safety) Analysis Set
5	14.1.1.5	Number of Patients by Site, Treatment Group, and Randomization Stratum Per Protocol (PP) Analysis Set
		Demographic and Baseline Characteristics
6	14.1.2.1	Demographics and Baseline Disease Characteristics Overall and By Treatment Group mITT (Randomized and Treated) Analysis Set
7	14.1.2.2	Demographics and Baseline Disease Characteristics Overall and By Treatment Group AT (Safety) Analysis Set
8	14.1.2.3	Demographics and Baseline Disease Characteristics Overall and By Treatment Group Per Protocol Analysis Set
9	14.1.2.4	Demographics and Baseline Disease Characteristics Overall and By Treatment Group Intent-to-Treat Analysis Set
10	14.1.3.1	Patients by Gender and Age Category Overall and by Treatment Group mITT (Randomized and Treated) Analysis Set
11	14.1.3.2	Patients by Gender and Age Category Overall and by Treatment Group AT (Safety) Analysis Set
12	14.1.3.4	Patients by Gender and Age Category Overall and by Treatment Group Per Protocol Analysis Set
		Summary of Baseline Microbiology
13	14.1.3.5	Pathogen (genus / species) in Blood Culture and Tissue Samples in ITT (Randomized) Subjects Overall and By Treatment Group
14	14.1.3.6	Pathogen (genus / species) in Blood Culture Specimens in ITT (Randomized) Subjects Overall and By Treatment Group
15	14.1.3.7	Pathogen (genus / species) in Intra-Abdominal Specimens in ITT (Randomized) Subjects Overall and By Treatment Group

Prior and Concomitant Medications		
16	14.1.4.1	Number (%) of Patients with Prior Non-Antimicrobial Medications or Non-Nephrotoxic Medications by Category and Specific Medication Overall and By Treatment Group As Treated (Safety) Analysis Set

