68	14.3.1.4	Incidence Rates (%) and Event Counts of Drug-Related* TEAEs by System Organ Class and Preferred Term As Treated (Safety) Analysis Set†
69	14.3.1.5	Incidence Rates (%) and Event Counts of Serious TEAEs by System Organ Class and Preferred Term As Treated (Safety) Analysis Set†
70	14.3.1.6	Incidence Rates (%) and Events Counts of Serious TEAEs Sorted by Descending Incidence of Preferred Term in Subjects Receiving Reltecimod As Treated (Safety) Analysis Set†
71	14.3.1.7	Incidence Rates (%) and Events Counts of Serious Drug-Related* TEAEs by System Organ Class and Preferred Term As Treated (Safety) Analysis Set†
71	14.3.1.8	Incidence Rates (%) and Events Counts of Severe TEAEs by System Organ Class and Preferred Term As Treated (Safety) Analysis Set†
72	14.3.1.9	Incidence Rates (%) and Events Counts of Severe TEAEs Sorted by Descending Incidence of Preferred Term in Subjects Receiving Reltecimod As Treated (Safety) Analysis Set†
73	14.3.1.10	Counts of Drug-Related* TEAEs by Severity, System Organ Class, and Preferred Term Reltecimod 0.5 mg/kg As Treated (Safety) Analysis Set†
74	14.3.1.11	Counts of Drug-Related* TEAEs by Severity, System Organ Class, and Preferred Term Placebo As Treated (Safety) Analysis Set†

		Laboratory Data
75	14.3.2.1	Screening, Day 7, Day 14, and Changes from Screening Blood Chemistry by Treatment Group As Treated (Safety) Analysis Set†
76	14.3.2.2	Blood Chemistry Panel Shift Tables Summarizing Changes in Test Status from Screening (Baseline) to Day 7 or Early Discontinuation As Treated (Safety) Analysis Set†
77	14.3.2.3	Blood Chemistry Panel Shift Tables Summarizing Changes in Test Status from Screening (Baseline) to Day 14 or Early Discontinuation As Treated (Safety) Analysis Set†
78	14.3.2.4	Blood Chemistry Frequencies By Visit With Respect To Normal Ranges and Critical Values by Treatment Group As Treated (Safety) Analysis Set†
79	14.3.2.5	Creatinine Values at Screening and at Days 1, 2, 3, 7, 10, 14, 21, 29, and 90 by Treatment Group As Treated (Safety) Analysis Set†
80	14.3.2.6	Summary of Potential Drug Induced Liver Injury (DILI) By Treatment Group As Treated (Safety) Analysis Set†
81	14.3.3.1	Screening, Days 1, 2, 3, 7 and 14, and Changes from Screening Blood Hematology by Treatment Group As Treated (Safety) Analysis Set†
82	14.3.3.2	Blood Hematology Panel Shift Tables Summarizing Changes in Test Status from Screening (Baseline) to Day 7 Early Discontinuation

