83	14.3.3.3	Blood Hematology Panel Shift Tables Summarizing Changes in Test Status from Screening (Baseline) to Day 14 Early Discontinuation
84	14.3.3.4	Blood Hematology Frequencies by Visit with Respect to Normal Ranges and Critical Values by Treatment Group As Treated (Safety) Analysis Set

85	14.3.4.1	Screening, Days 1, 3, 7, 14, 29 and 29 and Changes from Screening Urinary albumin/creatinine ratio by Treatment Group As Treated (Safety) Analysis Set†
86	14.3.4.2	Incidence of chronic kidney disease (CKD) at Day 90 by Treatment Group As Treated (Safety) Analysis Set†
		Vital Signs
87	14.3.5.1	Vital Signs at Screening, Day 1, Day 2, Day 3, Day 7, Day 14, Day 21, Day 29 and Changes from Screening By Treatment Group As Treated (Safety) Analysis Set†

12 Appendix 2: AE Listings

		AE Listings
1	16.2.7.1	All TEAEs Sorted by Specific AE by Treatment Group, Sorted by SOC and PT As Treated (Safety) Analysis Set
2	16.2.7.2	All TEAEs Sorted by Specific AE by Treatment Group, Sorted by Patient ID and Onset As Treated (Safety) Analysis Set
3	16.2.7.3	Drug-Related TEAEs Sorted by Specific AE by Treatment Group, Sorted by SOC and PT As Treated (Safety) Analysis Set
4	16.2.7.4	Serious TEAEs Sorted by Specific AE + by Treatment Group, Sorted by SOC and PT As Treated (Safety) Analysis Set
5	16.2.7.5	Serious Drug-Related TEAEs Sorted by Specific AE by Treatment Group, Sorted by SOC and PT As Treated (Safety) Analysis Set
6	16.2.7.6	All TEAEs with Outcome of Death Sorted by Specific AE by Treatment Group, Sorted by SOC and PT As Treated (Safety) Analysis Set
7	16.2.7.7	All TEAEs with Outcome of Drug-Related Death Sorted by Specific AE by Treatment Group, Sorted by SOC and PT As Treated (Safety) Analysis Set
8	16.2.7.8	All TEAEs with Outcome of Study Drug Discontinuation Sorted by Treatment Group, SOC, and PT As Treated (Safety) Analysis Set
9	16.2.7.9	All TEAEs with Outcome of Discontinuation from Study Sorted by Treatment Group, SOC, and PT As Treated (Safety) Analysis Set
10	16.2.7.10	Day 0 AE's Sorted by SOC and PT As Treated (Safety) Analysis Set

13 Appendix 3: Patient Listings

		Patient Listings
	16.2.8.1	Form: Randomization and Administration
	16.2.8.2	Form: Demographics
	16.2.8.3	Form: Abdominal Sepsis
	16.2.8.4	Form: Abdominal Sepsis Information
	16.2.8.5	Form: Primary Infection Site Assessment
	16.2.8.6	Form: Initial Source Control
	16.2.8.7	Form: Follow-Up Source Control
	16.2.8.8	Form Acute Kidney Injury
	16.2.8.9	Form: Inclusion/Exclusion

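### SAP 6.3 names the wrong visits for physical exam data and, with SAP 9.6, replaces the protocol's Normal/Abnormal tabulation with listings

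*SAP*

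**What the plan says.** SAP section 6 lists the exam among the main safety outcomes: "The primary safety measures are AEs (including SAEs), deaths, clinical safety laboratory, PE, and vital signs through Day 29". It adds that "The safety profiles will be compared between active and placebo groups using descriptive statistics as appropriate for continuous and categorical safety variables". Protocol 12.12 likewise names it: "The primary safety measures are AEs (including SAEs), clinical safety laboratory, PE, vital signs through Day 28".

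On how exam results are reported, the two documents differ:

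- Protocol 12.12: "Results from PEs will be tabulated for the Screening, Day 7, and Day 14". It goes on to ask for the number of patients evaluated and the count and percentage Normal and Abnormal. The protocol synopsis has the same rule.
- SAP 6.3: "Physical exam data on Days 1, 7, and 10 will be summarized in patient specific listings".
- SAP 9.6: "Results from physical examinations will be provided in the patient listings".

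SAP section 1 states that the SAP governs where the two documents differ.

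Two table titles in SAP Appendix 1 also bear on visit days. Table 14.3.3.1 is titled "Screening, Days 1, 2, 3, 7 and 14, and Changes from Screening Blood Hematology by Treatment Group". Table 14.3.4.1 is titled "Screening, Days 1, 3, 7, 14, 29 and 29 and Changes from Screening Urinary albumin/creatinine ratio by Treatment Group".

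**The concern.** There are two separate faults. First, the days in SAP 6.3 do not match when full exams are done. A programmer following that sentence would take two visits at which an exam happens only if symptoms prompt it, and would pass over the pre-dose exam and the Day 14 exam. Second, listings replace a tabulation, although SAP section 6 still says that safety profiles will be compared between groups. Because the SAP prevails, the protocol's table drops out, and the SAP gives no reason.

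A reader of the report would then have no count of how many patients were examined per arm at each visit, no proportion abnormal, and no baseline proportion to set it against.

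**Working it through.** No arithmetic beyond counting applies. The check sets the visit days side by side.

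**Physical exams**

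| Source | Days |
|---|---|
| Full exam, protocol Appendix A | Screening, 7, 14 |
| Full exam, SAP Appendix 5 | Screening, 7, 14 |
| Symptom-driven interim exam, both schedules | 1, 3, 10 |
| Tabulation, protocol 12.12 and synopsis | Screening, 7, 14 |
| SAP 6.3 | 1, 7, 10 |

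1. The overlap between SAP 6.3 and the full-exam visits is Day 7 alone, 1 of 3. Screening and Day 14 are not named.
2. Days 1 and 10, 2 of the 3 days named, are interim-exam visits. Protocol 7.3 also limits the Day 10 visit to patients still in hospital.
3. Day 1 cannot be read as a baseline. Protocol 7.3 starts Day 1 at study drug administration, and SAP 6 and 6.4 use Day 0 as a label separate from Day 1.
4. SAP 6.3 therefore conflicts with the SAP's own Appendix 5 as well as with the protocol.

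**Planned outputs.** The safety tables in SAP Appendix 1 end with vital signs (Table 14.3.5.1), so the number of exam tables is 0. The shift tables in SAP 6.2.2 cover chemistry and hematology only. The exam outputs are patient listings 16.2.8.14 and 16.2.8.31 in SAP Appendix 3, and neither states visit days.

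**Appendix 1 titles**

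| Table | Scheduled after Screening | Title after Screening | Difference |
|---|---|---|---|
| 14.3.3.1 hematology | 1, 3, 7, 14, 29 (SAP 3.8, 9.2.3) | 1, 2, 3, 7, 14 | Day 29 missing (1 of 5); Day 2 added |
| 14.3.4.1 albumin/creatinine ratio | 1, 3, 7, 14, 29, Month 3 (SAP 3.8, 9.3) | 1, 3, 7, 14, 29, 29 | Month 3 missing (1 of 6); Day 29 printed twice |

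As titled, these two tables lose values and changes from Screening at Day 29 and Month 3 respectively.

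**The case against.** The strongest reply is that little is lost in practice, and parts of it stand.

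- A reader might infer that no exam finding is compared between arms or judged against baseline. The documents do not support that. SAP 6.2.3 and protocol 11.1.3 require a new or aggravated clinically relevant finding, relative to the baseline assessment, to be reported as an adverse event. Those from Day 1 on enter the treatment-emergent tables by arm. This route does not give the number examined, the baseline status or the proportion abnormal at a visit.
- A reader might infer that screening exams will not be reported at all. SAP 9.6 and the two listings carry no day restriction, and 16.2.8.14 sits among the screening forms, so raw screening exams may well be listed. What is missing is a baseline summary.
- A reader might infer that Day 29 hematology and the Month 3 albumin/creatinine ratio go untabulated. SAP 6.2.3 and Table 14.3.3.4 cover hematology against normal ranges at each visit, and Month 3 albuminuria can enter the Day 90 CKD table, 14.3.4.2. SAP 9.2.3 and 9.3 also state the correct days in the text.
- A reader might infer that Day 2 in the hematology title has no blood count behind it. Protocol 9.2.11.3 and the RNA-sample footnote in both schedules call for a blood count at that time in participants of the optional sub-study.
- A table at Days 7 and 14 would cover a selected group. Protocol 7.3 and 9.2.4 exempt outpatients seen by the visiting nursing service from the exam. That is correct, and it is a reason to show the number evaluated by arm.
- The protocol's tabulation sentence does not itself say by arm, and asks for neither a body-system breakdown nor a shift from Screening. The by-arm layout follows from the comparison between groups stated in protocol 12.12 and SAP section 6. The other two would be additions, so the fix leaves them out.

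None of these points reconciles the days in SAP 6.3 with SAP Appendix 5, or explains why the protocol's table was dropped.

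**Conclusion.** The point holds as a minor inconsistency in safety reporting. SAP 6.3 names one full-exam visit out of three, and under the SAP as written a named primary safety measure has no summary of its results by arm or at baseline. The two Appendix 1 titles each omit one scheduled visit from the values-and-changes table, with partial cover elsewhere.

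Alpha, power and the primary efficacy test are unaffected. The conclusion rests on two things: the schedule rows as printed in both documents, and the SAP's rule that it prevails. How much the report would lose depends on whether programming follows SAP 6.3 and the Appendix 1 titles, or the schedules and the SAP text; the documents do not settle that.

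**What to change.** Before unblinding:

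1. In SAP 6.3 and 9.6, name Screening, Day 7 and Day 14 as the exam visits.
2. Add to Appendix 1 the protocol's table in the As-Treated set: number evaluated and n (%) Normal and Abnormal, by arm, at those three visits. Footnote that outpatients seen by the visiting nursing service have no Day 7 or Day 14 exam. If the sponsor prefers listings only, state and justify the departure from protocol 12.12.
3. Keep the Day 1, 3 and 10 interim exams as a listing.
4. In the Table 14.3.3.1 title, add Day 29, and either remove Day 2 or mark it as sub-study participants only, in line with SAP 9.2.3.
5. In the Table 14.3.4.1 title, replace the repeated 29 so that it reads Day 29 and Month 3, in line with SAP 9.3.

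The cost is one added safety table, edits to two SAP sections and two corrected titles. No new data or procedures are needed.

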6.4 Vital Signs

Vital signs including weight, temperature, systolic BP, diastolic BP, respiration rate, and heart rate will be summarized across time (Day 0, Day 1, Day 2, Day 3, Day 7, Day 10, Day 14, Day 21, and Day 29), separately by treatment group using N, Mean, and SD. Vital signs will be summarized for the Safety Analysis Set.

7 Presentation of Enrollment and Baseline Characteristics

7.1 Site Specific Numbers of Patients by Analysis Set

Table 14.1.1.1 summarizes the numbers of patients screened and for each analysis set by site.

Table 14.1.1.2 summarizes the numbers of patients by site, analysis set, and treatment group.

Table 14.1.1.3 summarizes the numbers of patients by site, treatment group, and randomization stratum in the mITT Analysis set. The primary efficacy analyses will be performed in the mITT analysis set.

Randomization strata are defined as follows:

- **Acuity of AKI:** whether or not AKI is diagnosed at time of presentation of abdominal infection or during the 48 hours following the suspected diagnosis of abdominal infection.
- **Subject Age :** ≥ 18 to ≤ 75 or > 75 to ≤ 85 years old.

Table 14.1.1.4 provides the same summary for the As Treated (primary Safety) analysis set.

Table 14.1.1.5 provides the same summary for the PP (secondary efficacy analysis set).

Totals across all sites will be provided for these tables.

